6.6.4 Procedure for discontinuation of treatment

If a patient permanently discontinues treatment, the date and reason for discontinuation (if known) will be documented in the eCRF.

After discontinuation of treatment in a patient, the patient will continue in the study and should be followed-up as described above ([Section 6.6.3](#)).

6.6.5 Replacements

Re-screening is allowed.

Patients that are withdrawn or discontinued during the study will not be replaced or re-entered into the study.

6.6.6 Sponsor termination of study

Although the Sponsor has every intention of completing the study, the Sponsor reserves the right to discontinue the study at any time for clinical or administrative reasons. In such a case, the Investigator will be informed of additional procedures to be followed to ensure that adequate consideration is given to the protection of the patient's interest. Breaking of the treatment code (unblinding) will be performed and the Investigator will be informed.

If the study is prematurely terminated or suspended for any reason, the Investigator has to inform the patients and to assure appropriate patient follow-up, including give information regarding treatment received. The Sponsor should promptly inform the study site, and the RA/CA on the termination or suspension and the reason(s) for the termination or suspension. The IEC should also be informed promptly and provided with the reason(s) for the termination or suspension by the Sponsor or by the Investigator, as specified by the applicable regulatory requirements.

7 TREATMENTS

7.1 Treatment groups

Patients in this study will receive the test product Gedea Pessary

[figure not shown]
[figure not shown]
In the study, 26 patients will be treated with Gedea Pessary to be self-administered daily for 6 days (Day 0 to Day 5).

7.2 Identity of the investigational product

7.2.1 Test product/Gedea Pessary

The test product, Gedea Pessary (commercial name *p*Hyph), is a Class IIb medical device according to MDR 2017/745, containing 150 mg GDL and 184 mg NaG.

Gedea Pessary is a white, convex, bullet-shaped pessary, approximately 17 mm in length, to be administered vaginally with a CE-marked pessary applicator (Schägner GmbH, Steinmauern, Germany) ([Figure 2](#) and [Figure 3](#)).

Figure 2 Gedea Pessary and the Gedea Pessary blister package**Figure 3 Vaginal tablet applicator**

CE  Schägner GmbH
D-76479 Steinmauern

7.2.2 Manufacturing, packaging and labelling of investigational product

Gedea Biotech AB is the responsible manufacturer of the investigational products (Gedea Pessary). Gedea Biotech AB has subcontracted production, packing, labelling and release testing of the clinical investigation material for use in the clinical investigation to Galenica AB (Malmö, Sweden). Batch release is performed by Gedea Biotech AB Quality Assurance Director.

The investigational products will be packed in blister packs containing 6 pessaries packed together with 6 pessary applicators in a cardboard box (Figure 2 and Figure 3). The cardboard box will be labelled with “Gedea Pessary pHyp”, batch number, study number, package number, manufacturing date and expiry date. The label used in the study will be written in the local language.

Labels will be prepared in accordance with good manufacturing practice (GMP), the Medical Devices Directive 93/42/EEC and local regulatory guidelines.

7.2.3 Stability program

The stability of Gedea Pessary pHyp pessaries has been evaluated and confirmed in a technical stability study at the conditions 25°C (up to 9 months, as of May 2021) and 40°C (up to 6 months) and in a clinical stability study, confirming stability up to 6 months at the conditions 25°C and 40°C. The stability program is planned up to 36 months, and extension

of shelf life will be done accordingly. For further information, refer to the Investigator's Brochure (IB).

7.2.4 Storage and handling of investigational products

The investigational products Gedea Pessary will be stored at room temperature (15°C--25°C) and protected from direct sunlight or freezing. The investigational products *must not* be used outside of the study. For further information, refer to the IB.

It is the responsibility of the Investigator to ensure that the investigational product is stored in its original packaging in a secure location with access only by authorised personnel, separate from other medications. The temperature should be noted daily (working days only unless automatic temperature readings are available).

7.2.5 Doses and treatment regimens

Each patient will self-administer a total of 6 doses of Gedea Pessary in the study. The pessary is slow-release formulated, administering 150 mg GDL and 184 mg NaG, over 24 hours.

The pessary will be self-administered vaginally by the patient at night, before going to bed. Instructions for use will be distributed at the first visit, advising patients on how to use the product together with the applicator. The patients will also be trained by site personnel in how to use the product, no previous experience of use is needed.

Briefly, patients will be instructed to wash their hands and vaginal area prior to use; place a tablet into the applicator and insert as far into the vagina as is comfortable (without forcing), or until half of the applicator is inside; discard the applicator after use; not use tampons or other vaginal products while using this product.

7.3 Investigational product accountability

The Investigator is responsible for full traceability of the investigational product from the manufacturer to patients until return or disposal. This shall be ensured by use of product accountability records, documenting quantity at storage and deliveries to and from storage.

Shipping records of investigational product deliveries from the manufacturer shall be kept at study sites, including *at least* the following information

- Investigational product name and quantity received
- Delivery date
- Batch number
- Expiry date

Dispensing logs shall be kept at study sites, documenting *at least* the following information:

- Investigational product name
- Batch number
- Expiry date
- Dispense date
- Number of units dispensed
- Patient (patient number) receiving the investigational product
- Number of units remaining in stock

Patients will be asked to return all used and not used treatment packages.

Any non-functioning investigational products or applicators shall be documented. All returned, unused or expired investigational products must be returned to the Sponsor for destruction unless otherwise stated in writing by the Sponsor. Any used or opened unused materials *must not* be reused.

7.4 Method of assigning patients to treatment groups

Not applicable.

7.5 Additional products and material

7.5.1 Additional material

The Sponsor will provide the study sites with study specific kits containing vaginal swabs for culture and sequencing of the vaginal microbiome. The kits will be developed specifically for the study and include all material needed as well as instructions and pre-paid envelopes where applicable.

Study sites will provide pH-test strips and urine dipstick pregnancy tests (urinary human chorionic gonadotropin [U-HCG]). pH-test strips and urine dipsticks used as per clinical routine at the site may be used.

The Investigator is responsible for full traceability of the vaginal swabs from the manufacturer to patients until return or disposal. This shall be ensured by use of accountability records documenting quantity at storage and deliveries to and from storage.

Shipping records of vaginal swab kit deliveries from the manufacturer shall be kept at study sites, including at least the following information.

- Swab kit batch number and quantity received
- Delivery date
- Expiry date

Dispensing logs shall be kept at study sites, documenting *at least* the following information.

- Swab kit batch number
- Expiry date
- Dispense date
- Number of units used
- Patient receiving the swab kit
- Number of units remaining in stock

All unused or expired swab kits must be returned to the Sponsor for destruction unless otherwise stated in writing by the Sponsor. Any used, or opened unused materials *must not* be reused.

7.5.2 Rescue medication

On Days 7 and 14, patients having VVC symptoms of the same or higher intensity compared to the inclusion visit (Day 0), will be offered rescue treatment, if considered necessary. For

details on VVC symptom score see [Section 9.1.2](#) Rescue treatment will be according to standard clinical routines, as described below.

Patients will receive a prescription of fluconazole (50-150 mg as a single dose, orally) or Clotrimazole pessary (500 mg as a single dose, intra-vaginally) and if necessary, topical treatment with 1% clotrimazole or 1% clotrimazole/1% hydrocortisone. Rescue medication will not be provided by the Sponsor, however the Sponsor will reimburse the cost.

In addition, patients with recurrence or persistent symptoms on Day 25 (i.e. symptoms recurred on Day 25) may also be offered rescue treatment, according to the standard clinical routines mentioned above. The site will decide whether a visit to the clinic is needed and if rescue medication should be prescribed.

Patients taking rescue medications prior to the visit where clinical cure is assessed (Day 7 or Day 14), will be considered in the statistical analysis as described in [Section 12](#). In general, these patients should stay in the study and continue to be followed-up.

The use of any rescue medication will be recorded in the eCRF.

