3 INTRODUCTION

3.1 Indication

Vaginal infection is a huge and largely underestimated problem, affecting 70% to 75% of women at some point in their life, and 5% to 8% of adult women have recurrent vulvovaginal candidiasis (VVC) with ≥ 4 episodes yearly.^{1,2}

The vaginal microbiome is a dynamic system, composed of a complex mixture of microorganisms in different ratios and quantities, which depend on lactic acid producing bacteria to maintain a weakly acidic environment.³ Changes to vaginal microflora increase the pH, thereby forming a favourable environment for vaginal pathogens. Vaginal or systemic antibiotics treatment is frequently followed by VVC, likely due to the elimination of the protective bacterial flora, thereby allowing *Candida* overgrowth.⁴⁻⁸ Infections are also facilitated due to the mucosal effect of increased oestrogen levels and a weakened immune system during pregnancy.⁹ Recurrences are more common in pregnant women, and their therapeutic response is reduced compared to non-pregnant women.^{10,11} Further, contraceptive pills, menstruation, and diabetes mellitus have been identified as predisposing factors for VVC.^{12,13} *Candida albicans* is the most prevalent pathogen, which, according to epidemiological studies, is present in between 73% and 92% of vaginal isolations.¹⁴ *Candida glabrata* is the second most prevalent pathogen.¹⁴

Many women diagnose themselves with VVC and purchase over the counter (OTC) anti-mycotic treatments. However, many misdiagnose themselves and therefore receive unnecessary or inappropriate treatment.¹⁵ In a study of 95 symptomatic women who purchased OTC anti-mycotics for treatment of presumed VVC, only 34% of them were actually diagnosed with VVC.¹⁶ The most common other diagnoses were bacterial vaginosis (BV; 18.9%), mix of BV and VVC (18.9%), and normal (13.7%).

Current treatment strategies for uncomplicated or acute VVC include anti-mycotic vaginal creams or pessaries/vaginal tablets, such as econazole, clotrimazole, or miconazole for 1 to 7 days, or single-dose oral fluconazole. Reported clinical cure rates are variable, which may reflect different clinical cure definitions between studies. Clinical cure rates after 27 to 38 days of intravaginal imidazole treatment (clotrimazole, terconazole, butoconazole, or

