4.2.1 Secondary endpoints

1. Safety and tolerability, based on reported treatment-emergent AEs (safety endpoint).
2. Proportion of patients having a continued clinical response to treatment at Day 25, defined as the proportion of patients clinically cured on Day 7-14 and thereafter responding “no” to the yes/no question, “Have the symptoms recurred?”
3. Proportion of patients having a cure defined as clinical cure Day 7-14 according to primary endpoint and mycological cure (culture negative for growth of *Candida* species).
4. Proportion of patients having a reduction in CVVS score on Day 7-14 compared to Day 0.
5. Change in the CVVS score from Day 0 to Day 7-14.
6. Proportion of patients having a reduction in the sum of the 3 vulvovaginal symptoms scores (itching, burning, and irritation) on Days 1-7, Day 11, Day 14 and Day 25, compared to Day 0.
7. Change in the sum of the 3 vulvovaginal symptoms scores (itching, burning, and irritation) on Days 1-7, Day 11, Day 14 and Day 25, compared to Day 0.
8. Proportion of patients having a mycological cure as assessed by vaginal culture on Day 7-14 and Day 25.
9. Proportion of patients having an absence of *Candida* hyphae in the wet smear on Day 7-14.
10. Usability, measured by patient questionnaire, on Day 6.

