8.4 Prior and concomitant medications

Information about any concomitant medication, including OTC medications and vitamins used by patients within 14 days prior to inclusion and during the study, shall be collected at all site visits (Day 0 and Day 14) for all patients and also at the telephone contacts (Day 7 and Day 25). The generic name or trade name, dosage and reason for use shall be recorded in the eCRF for all medications.

NOTE:

VVC-treatment or any anti-fungal therapy unrelated to VVC within 14 days prior to inclusion, is not allowed (see [Section 6.4](#)).

During the study, anti-fungal therapy and other treatments related to VVC should be avoided (unless rescue treatment at Day 14) (see [Section 6.5](#)).

See further information on rescue medication in [Section 7.5.2](#).

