12.4.2 Primary endpoint analysis

In the estimand setting, the primary endpoint will, in addition to the definition stated in [Section 4.1.1](#), take the following identified intercurrent events into account:

1. Concomitant anti-fungal therapy or other treatments related to VVC due to lack of clinical performance prior to CVVS evaluation used for the primary endpoint definition.
2. Treatment discontinuation due to lack of clinical performance.
3. Rescue medication prior to the CVVS evaluation used for the primary endpoint definition.

Applying the composite strategy to account for these intercurrent events, these have been incorporated in the endpoint definition. Thus, to be defined as clinically cured on Day 7-14, the patient needs to have the last available CVVS score equal to or below 3 at Day 7-14, and that none of the above stated intercurrent events have occurred. If the CVVS score is above 3, or any of the intercurrent events has occurred, the patient is defined as not clinically cured on Day 7-14.

Patients with missing CVVS score at Day 7-14 and no intercurrent events will be considered as missing in the analysis.

The primary endpoint clinical cure rate on Day 7-14, as defined in the section will be calculated and presented together with a one-sided 95 % CI based on the Wilson score.

The primary performance objective of the trial is to show that the clinical cure rate is above 30 %, i.e. to show that the lower limit of the one-sided 95 % CI for the observed cure rate is above 30 %.

Hypotheses for the primary clinical performance endpoint

Null hypothesis: Clinical cure rate is less than or equal to 30 %.

Alternative hypothesis (one-sided): Clinical cure rate is above 30 %.

Sensitivity analyses to evaluate the effect of missing data for any of the 6 individual vulvovaginal signs and symptoms scores included in the CVVS score will be performed. Details on the sensitivity analyses will be described in the SAP.

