6.2.2 Restrictions

During the study, the following medications are not allowed and should be avoided:

1. Anti-fungal medication related to VVC – explicitly anatomical therapeutic chemical (ATC) codes J02A and D01AC.
2. Other treatments for VVC (e.g. probiotics like Candicur and Multigyn).

Since use of concomitant anti-fungal therapy or other treatments related to VVC due to lack of efficacy prior to CVVS evaluation used for the primary endpoint definition is considered an intercurrent event, a review of all concomitant medication will be performed prior to data base lock to classify the concomitant medication as an intercurrent event or not.

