7.9.3 Secondary Performance Variables

All secondary clinical performance endpoints will be presented with descriptive statistics. The following binary secondary clinical performance endpoints will show the endpoint estimate together with a two-sided 95% CI based on the Wilson score.

- Proportion of patients having a continued clinical response to treatment at Day 25, defined as the proportion of patients clinically cured on Day 7-14 (taking into account the intercurrent events and applying the composite strategy as described in Section 7.9.1) and thereafter responding "no" to the yes/no question, "Have the symptoms recurred?" and no rescue medication has been given up to day 25
- Proportion of patients having a cure defined as clinical cure Day 7-14 according to primary endpoint (taking into account the intercurrent events and applying the composite strategy as described in Section 7.9.1) and mycological cure at Day 7-14 (culture negative for growth of Candida species).
- Proportion of patients having a reduction in CVVS score on Day 7-14 compared to Day 0.
- Proportion of patients having a reduction in the sum of the 3 vulvovaginal symptoms scores (itching, burning, and irritation) on Days 1 to 7, Day 11, Day 14 and Day 25, compared to Day 0.
- Proportion of patients having a mycological cure as assessed by vaginal culture on Day 7-14 and Day 25.
- Proportion of patients having an absence of Candida hyphae in the wet smear on Day 7-14.

Statistical Analysis Plan

Study ID: CL4

Presentation of the continuous secondary clinical performance endpoints below will include the two-sided 95% CIs for the arithmetic mean.

- The change in CVVS score from Day 0 to Day 7-14 (last available assessment).
- Change in the sum of the 3 vulvovaginal symptoms scores (itching, burning, and irritation) to each post baseline assessment.

Usability will be measured on Day 6, by a patient questionnaire (see Appendix 1). The questionnaire contains 2 yes/no (i.e. binary) variables, 2 categorical variables and the question, "How do you generally regard the treatment?", rated on a 1-10 integer scale. These endpoints will be presented descriptively, treating the question rated on the 1-10 scale as a continuous variable. In case of multiple assessments of usability, the first non-missing value will be used.

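### Rescue is the only treatment after the Day 7-14 cure assessment that voids continued clinical response at Day 25, so a woman who obtains her own VVC treatment and reports no recurrence can count as a responder

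*Protocol*

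**What the plan says.** Protocol 4.2.1 defines continued response as cure at Day 7-14 and "thereafter responding “no” to the yes/no question, “Have the symptoms recurred". Section 4 refers the reader to 12.4 for the final definitions. There, protocol 12.4.3.2, and SAP 7.9.3 in the same terms, add a third condition: "and no rescue medication has been given up to day 25".

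Protocol 7.5.2 describes rescue as something the site gives. On Days 7 and 14, women whose symptoms are at least as intense as on Day 0 "will be offered rescue treatment, if considered necessary", and "Patients will receive a prescription of fluconazole (50-150 mg as a single dose, orally) or Clotrimazole pessary". At Day 25 the site decides whether to prescribe. SAP 6.2.1 follows the same pattern.

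Protocol 12.4.2 lists three intercurrent events for the primary endpoint. Rescue is the third. The first is separate from it: "Concomitant anti-fungal therapy or other treatments related to VVC due to lack of clinical performance prior to CVVS evaluation". SAP 7.9.2 repeats the list and adds that, for practical purposes, events 1 and 3 count as one. SAP 6.2.2 plans a pre-lock review of all concomitant medication, because such use "prior to CVVS evaluation used for the primary endpoint definition is considered an intercurrent event".

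Protocol 6.5 disallows anti-fungals and other treatments for VVC during the study. Protocol 8.4 collects "Information about any concomitant medication, including OTC medications and vitamins used by patients within 14 days prior to inclusion and during the study". SAP 7.2.3 defines a Day 25 per protocol set (PPAS25), and SAP 7.9 makes it supportive to the FAS.

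**The concern.** The added rescue clause shows what the sponsor intends: once a woman is treated again, her response no longer belongs to the pessary. The same reasoning applies to a product she obtains herself, but the clause names only rescue.

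The situation is plausible. Cure allows a CVVS of up to 3 and does not require a negative culture, so a cured woman may still have symptoms or *Candida*. She will usually be below the rescue trigger, which compares her symptoms with Day 0. Protocol 3.1 notes that "Many women diagnose themselves with VVC and purchase over the counter (OTC) anti-mycotic treatments". If she buys one, stays well and answers no at Day 25, the answer is truthful, but the pessary may not be what kept her well.

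The error can only raise the continued-response rate, and there is no control arm against which it would show.

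**Working it through.** **1. Which rule applies after the cure assessment.** The CVVS that decides cure is the last available one at Day 7-14. From there to Day 25 is nominally 25 − 7 = 18 days, or 25 − 14 = 11 days when the Day 14 score is used. Protocol 12.4.2 and SAP 7.9.2 limit events 1 and 3 to the time before that CVVS. After it, the only statement about treatment in the endpoint definition is the rescue clause.

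**2. How women cured at Day 7-14 are classified in the FAS, read literally.**

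| After the cure assessment | Recurrence answer | Counted as |
|---|---|---|
| Site prescribes rescue | yes or no | non-responder |
| Treats herself | yes | non-responder |
| Treats herself | no | responder |
| No treatment | no | responder |

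Only the third row is in question.

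**3. The plan's own figure.** The documents state no expected rate for the Day 25 endpoint. The stated sample size concerns the primary endpoint and reproduces: n = [(z₀.₉₅√(p₀q₀) + z₀.₈₀√(p₁q₁))/(p₁ − p₀)]² with p₀ = 0.30 and p₁ = 0.54 gives [(1.645 × 0.4583 + 0.842 × 0.4984)/0.24]² = 23.90, rounded up to 24. The Day 25 definition does not enter this calculation.

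**4. Effect per woman.** With all 26 in the denominator, each reclassified woman moves the rate by 1/26 = 3.8 points; with 24 evaluable, by 1/24 = 4.2 points.

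**5. Illustration.** Both the starting count and the number of self-treaters are assumptions. One start is 14/26, the planned cure rate (0.54 × 26 = 14.04) with no loss by Day 25. The other is 12/26, which allows for some loss. Intervals are two-sided 95% Wilson, as SAP 7.9.3 specifies: [p + z²/2n ± z√(p(1 − p)/n + z²/4n²)]/(1 + z²/n), z = 1.96.

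| Self-treaters who answered no | Starting from 14/26 | Starting from 12/26 |
|---|---|---|
| 0 | 53.8% (35.5-71.2) | 46.2% (28.8-64.5) |
| 1 | 50.0% (32.1-67.9) | 42.3% (25.5-61.1) |
| 2 | 46.2% (28.8-64.5) | 38.5% (22.4-57.5) |
| 3 | 42.3% (25.5-61.1) | 34.6% (19.4-53.8) |

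**6. What PPAS25 would do.** Exclusion removes a woman from the numerator and the denominator. With one self-treater among 14 responders, exclusion gives 13/25 = 52.0%, and counting her as a non-responder gives 13/26 = 50.0%. With three, the figures are 11/23 = 47.8% and 11/26 = 42.3%.

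**The case against.** The strongest reply is that the documents already treat the two kinds of treatment as one. SAP 7.9.2 equates events 1 and 3 for this study as a whole, without naming an endpoint. Protocol 7.5.2 also speaks of women taking rescue before the Day 7 visit, when the site has not yet offered any, so the word is sometimes used more broadly than site prescription. This part stands: the text is ambiguous, not plainly silent. It does not settle the matter, because the equating sentence sits in the primary-endpoint section and both events it joins end at the primary CVVS.

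A second reply is that self-treatment is disallowed, so it is a protocol deviation, and PPAS25 was added for deviations that affect Day 25. That is correct, and a reader who inferred that no rule touches such use would go too far. But section 6.5 attaches no consequence for the endpoint, and PPAS25 is supportive, depends on a clean-file decision, and excludes the woman rather than counting her as a non-responder.

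A third reply concerns the review in SAP 6.2.2. It covers all concomitant medication, so it would be wrong to say that it stops at the cure visit. What is time-limited is the event it is meant to classify.

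Finally, the number of women affected is speculative. Protocol 3.1 describes women in general. It gives no rate for cured participants who have been told not to use anti-fungals and who report no recurrence. That stands, and the table in the working is not a forecast.

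**Conclusion.** The gap is real but narrow. As written, a woman cured at Day 7-14 who then obtains her own VVC treatment and reports no recurrence can be counted as a continued response in the main FAS analysis. The bias is upward, at 3.8 points per woman if all 26 are in the denominator. This rests on the literal reading of rescue as site-prescribed and on the SAP's merging of events not reaching past the primary CVVS.

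Three stronger readings are tempting but not supported. The first is that nothing but rescue voids the response: a yes on recurrence also does, so a woman who self-treats because symptoms returned, and says so, is already a non-responder. The second is that this is the trial's only Day 25 evidence of benefit: the symptom sums (endpoints 6 and 7) and mycological cure (endpoint 8) are also reported at Day 25. The third is that the trial's conclusion is at risk: the endpoint is secondary and descriptive, without a hypothesis or threshold, so the primary result and the sample size of 24 are unchanged.

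The wording should be corrected, since the repair is cheap and follows the sponsor's own principle.

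**What to change.** In protocol 12.4.3.2 and SAP 7.9.3, replace the rescue clause with: *no rescue medication, and no other anti-fungal or other treatment taken for VVC, prescribed or self-obtained, after the CVVS used for the primary endpoint and up to the Day 25 contact*. State that a woman with any such treatment is counted as not having a continued response. Keep the link to VVC, so that an anti-fungal for an unrelated condition does not make her a non-responder. In SAP 6.2.2, have the pre-lock review classify these treatments up to the Day 25 contact.

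The cost is one clause in each document and a slightly longer review. Over-the-counter use and the reason for it are already recorded under protocol 8.4, including at the Day 25 contact. The reported rate may be slightly lower.

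Separately, protocol 7.5.2 and SAP 6.2.1 state the oral fluconazole rescue differently (50-150 mg and 50 mg). The passages must be reconciled; this does not bear on the point above.
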